
credentialed Qualtrics links provided to them by the study staff. Our study staff is experienced in implementing Qualtrics surveys remotely in prior studies and has extensive experience providing brief intervention for caffeine reduction using the manual-only approach. These data will support feasibility and initial efficacy of future randomized controlled trials in populations experiencing specific caffeine-related problems.

2. Objectives (include all primary and secondary objectives)

Primary objective. Determine to what extent participants will engage with a remote caffeine reduction intervention for caffeine-related problems and find it acceptable.

Secondary objective (a). Determine to what extent participants are successfully able to reduce their caffeine consumption following the remote intervention.

Secondary objective (b). Determine to what extent participants report improvement in common caffeine-related problems (e.g., insomnia, anxiety, gastrointestinal distress) following the remote intervention.

Secondary objective (c). Determine whether participants randomized to the immediate intervention group (at 7-weeks post enrollment and post-treatment) show greater caffeine reductions or greater improvements in caffeine-related problems relative to the delayed treatment group at 7-weeks post-enrollment (prior to delayed treatment). This randomization will allow us to compare the initial efficacy of our intervention with caffeine reductions that may occur spontaneously over the same duration.

3. Background (briefly describe pre-clinical and clinical data, current experience with procedures, drug or device, and any other relevant information to justify the research)

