Community Observer. During the screening or treatment visit, participants will be asked to provide the name and contact information (phone number and email address; email will be the preferred method of contact) for a family member, friend, roommate, or significant other for the purposes of online surveys about their caffeine use. The participant will be asked to confirm with their observer that the study team has permission to contact them. The observer will be contacted twice to complete a brief online survey regarding the participants' caffeine use. The first contact will occur soon after the participant has the *Treatment* visit. The second contact will occur near the time of the participant's *Week 7 follow-up* visit.

Treatment Televisit. Participants determined to be eligible following the screening televisit will be scheduled to complete the treatment televisit shortly after screening. For the immediate treatment group, the treatment the *Treatment* visit will generally occur within one week of the screening televisit. The delayed treatment group will have their *Treatment* visit scheduled for a date approximately 7 weeks after screening. During the *Treatment* televisit, study staff will provide the participants with a digital copy of the caffeine reduction treatment manual used in prior studies (Evatt et al., 2016; Sweeney et al., 2019). As in prior research (Sweeney et al., 2019), study staff will give a brief (i.e., generally less than five minutes) description of the manual and instructions on how to gradually reduce their caffeine consumption over a period of six weeks. Participants will also complete assessments to determine their caffeine consumption and cigarette use over the past 7 days as outlined in Table 1. Participants will also be provided with information about their follow-up visits and how to complete weekly surveys.

Weekly Surveys. At seven days following the treatment televisit, participants will receive a request to complete a survey via Qualtrics link sent via email/text. The survey will consist of standard assessments of anxiety, depressed mood, sleep problems, gastrointestinal problems, past week caffeine/cigarette intake, and problems related to caffeine as outlined in Table 1. They will receive a request to complete the same survey once per week (weeks 1-6) until the Week 7 follow-up televisit.

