5. Any medical condition that, in the opinion of the investigators, may interfere with or preclude completion of the study

6. Drugs/ Substances/ Devices

- a. The rationale for choosing the drug and dose or for choosing the device to be used.

There are no proposed drugs or devices in the proposed research study.

- b. Justification and safety information if FDA approved drugs will be administered for non-FDA approved indications or if doses or routes of administration or participant populations are changed.

N/A

- c. Justification and safety information if non-FDA approved drugs without an IND will be administered.

N/A

7. Study Statistics

- a. Primary outcome variable.

To determine to what extent participants will engage with a remote caffeine reduction intervention for caffeine-related problems and find it acceptable (*Primary objective*), we will calculate the percentage of completed assessments for each televisit (Treatment, 7 Week Follow-Up, 14 Week Follow-Up) among eligible participants, as well as self-reported agreement with the items on the treatment acceptability survey completed at the 7 Week Follow-Up televisit (e.g., “I read all or most of the Guide to Caffeine Reduction and Cessation,” “Overall, the guide was helpful during my attempt to reduce or quit caffeine.”)

- b. Secondary outcome variables.

To determine to what extent participants are successfully able to reduce their caffeine consumption following the remote intervention (*Secondary objective (a)*), we will assess caffeine consumption as determined by the caffeine surveys at 7-and 14-week post-treatment follow-ups and compare this with consumption at the screening and treatment televisits.

To determine to what extent participants report improvement in common caffeine-related problems (e.g., insomnia, anxiety, gastrointestinal distress) following the remote intervention (*Secondary objective (b)*), we will assess caffeine related problems, anxiety, sleep problems, and gastrointestinal distress via standardized measures (see Table 1) at 7 and 14 weeks post treatment follow-ups and compare this with scores on these assessments at the screening and treatment televisits.

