To determine whether participants randomized to the immediate intervention group show greater caffeine reductions or greater improvements in caffeine-related problems (*Secondary objective (c)*) at the 7-week follow-up relative to the delayed treatment group over the same time-period, we will compare all of the secondary outcome variables described above between the two treatment groups to compare our intervention relative to spontaneous reduction that may occur with the passage of time.

c. Statistical plan including sample size justification and interim data analysis.

Because the primary purpose of this study is to collect pilot and feasibility data rather than determine efficacy via randomized controlled trial, the statistical analysis will be primarily descriptive. Primary outcomes will be reported as the proportion of completed televisits among eligible participants as well as the mean and standard deviation agreement (visual analog scale) with items on the treatment acceptability survey. With respect to secondary outcomes, means and standard deviations for the standardized assessments in Table 1 will be calculated for screening, treatment, 7 Week Follow-Up and 14-Week Follow-Up visits, and we will also visually inspect individual subject data. With respect to comparisons between the immediate and delayed intervention group, we will use a mixed effects regression model with between-subjects factors of group, a within subjects factor of time, and a group x time interaction term. A power analysis indicates that with two groups, four measurements, an alpha of .05, a desired power of .95, correlation among repeated measures of .5, and conservatively estimating a small effect (e.g., partial eta squared = .02), a sample size of 100 will be sufficient to detect a treatment effect. Further, we will calculate Cohen's *d* and partial eta squared effect sizes using means and standard deviations for pre-and post-treatment for all secondary outcomes. These effect size calculations will be used to determine the necessary sample size for any future large-scale randomized controlled trials to assess clinical effects in different treatment populations. The desired sample size of 100 is also based on our laboratory's proven participant capacity for prior randomized clinical trials and long-term human laboratory studies (e.g., Evatt et al., 2016; Sweeney et al., 2017, Sweeney et al., 2019).

d. Early stopping rules.

8. Risks

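### Section 7.c bases its .95 power on four measurements, but the treated-versus-untreated comparison in objective (c) has two occasions; with the plan's own inputs, power there is about .81

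*Combined protocol and SAP*

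**What the plan says.** Section 7.c describes a mixed effects regression with group, "a within subjects factor of time, and a group x time interaction term". The time levels are not listed in that sentence. The power statement follows directly: "two groups, four measurements, an alpha of .05, a desired power of .95, correlation among repeated measures of .5", with partial eta squared .02 offered as an example of a small effect. It concludes that "a sample size of 100 will be sufficient to detect a treatment effect". It does not say which model term is tested or how the group difference is spread over the four measurements. No allowance for loss to follow-up is stated.

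Secondary objective (c) in Section 2 defines the randomized contrast as the immediate group after treatment "relative to the delayed treatment group at 7-weeks post-enrollment (prior to delayed treatment"). Section 7.b adds that the two groups are compared over the same period. Under Treatment Televisit in Section 4.a, the delayed group has that "visit scheduled for a date approximately 7 weeks after screening". Both follow-up televisits and the weekly surveys are timed from the Treatment televisit, not from enrollment.

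**The concern.** A power figure is useful only if its inputs match the test it supports. Four measurements fit the four televisits, but the delayed group serves as an untreated control only until its Treatment televisit at about week 7. Everything it provides later is post-treatment. If the .95 is read as the power of the immediate-versus-delayed comparison, a null group x time result would look more informative than it is. The effect sizes are also meant to inform later trials, so the statement of what this comparison could detect should be accurate.

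**Working it through.** **Occasions available.** By approximate weeks from screening, from Sections 4.a and 4.c:

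| Visit | Immediate | Delayed |
|---|---|---|
| Screening | 0 | 0 |
| Treatment | 0 to 1 | 7 |
| Week 7 follow-up | 7 to 8 | 14 |
| Week 14 follow-up | 14 to 15 | 21 |

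At most three occasions line up in time (about 0, 7 and 14), and by week 14 both groups have been treated. Matched by visit name instead, both groups are untreated at the first two visits and treated at the last two, so no treated-versus-untreated contrast exists. The weekly surveys start only after treatment and add no untreated occasion in the delayed group. The contrast in objective (c) is therefore the change from screening to about week 7 (immediate group: Week 7 follow-up; delayed group: Treatment televisit).

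**Inputs from 7.c.** alpha = .05, N = 100, r = .5, partial eta squared = .02, so f² = .02/.98 = .0204 and f = .143. **Assumed:** 1:1 allocation, equal correlations, complete data.

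**Formula.** Group x time test, noncentral F: λ = f²·N·m/(1 − r), df1 = m − 1, df2 = (N − 2)(m − 1), where m is the number of occasions.

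**The plan's own figure, m = 4.** λ = .0204 × 100 × 4/.5 = 16.33, df 3 and 294, power .936. Exactly .95 needs N = 108; rounding f up to .15 gives .957 at N = 100. The stated figure is thus reproduced to within rounding. The between-group main effect with the same inputs gives only .43, so the interaction is evidently the term that was powered.

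**Two occasions, same f.** λ = .0204 × 100 × 2/.5 = 8.16, df 1 and 98, power .808. In SD units, d = √(16 × .0204) = 0.571. With r = .5 the change score has variance 2(1 − r) = 1, so this is a 0.57 SD difference in change. Simulation gave .805.

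**If .02 described a four-occasion pattern.** For a group gap δ over four occasions, f² = Σ(δ − mean δ)²/16. Scaling each pattern to f² = .0204 and testing the single change from baseline to week 7, with λ = N·d²/[8(1 − r)], gives:

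| Gap over four occasions | d at week 7 (SD) | λ | Power, N = 100 |
|---|---|---|---|
| Full gap at two | 0.571 | 8.16 | .81 |
| Full gap at one or at three | 0.660 | 10.88 | .90 |
| 0, d, d/2, 0 | 0.689 | 11.87 | .93 |
| 0, d, d/2, d/2 | 0.808 | 16.33 | .98 |
| Linear growth, tested at the second occasion | 0.256 | 1.63 | .24 |

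Simulation for 0.66 SD gave .902.

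**Loss to follow-up.** With an assumed 20% loss (N = 80), .81 becomes .71 and .90 becomes .83.

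**The case against.** The strongest reply is that the plan fixes no effect pattern, so neither the size nor the direction of the discrepancy is settled. This stands. A gap of (0, d, d/2, d/2) gives .98 on two occasions, above the four-measurement .936. A reader might infer that this comparison cannot reach .95 at r = .5, or that .81 to .90 brackets its power. The documents support neither: .81 to .90 covers only gaps that are fully present or fully absent at each occasion.

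It can also be said that objective (c) and Section 7.b already place the comparison at 7 weeks over the same period. That is so. Only the model and power sentences fail to carry it through, which is why the fix is small. A mixed model would use the later visits as well, but in the delayed group these follow treatment and add no treated-versus-untreated occasion. A week-7 comparison adjusted for screening would give about .90 (0.57 SD) or .965 (0.66 SD), but 7.c names no such test.

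Finally, the study is a pilot with a mainly descriptive analysis, objective (c) is secondary, and N = 100 also rests on laboratory capacity. All of this stands and limits the consequence.

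**Conclusion.** Wrong as written, but minor. It is a mismatch between the power inputs and the contrast, not an arithmetic slip, since the four-measurement sum reproduces. For objective (c) the stated .95 is unsupported unless an effect pattern is given. With the plan's inputs carried directly to two occasions, power is about .81; under one alternative reading of the .02 it is about .90. Both figures assume 1:1 allocation, r = .5 and complete data.

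A reader might also infer that the trial is too small, because .95 on two occasions would need a total of 162 (0.57 SD) or 122 (0.66 SD). The documents do not support that criticism: the purpose is feasibility, and the size has a second, practical basis. The figures apply to caffeine consumption only.

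**What to change.** Keep N = 100.

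1. Name screening and about 7 weeks post-enrollment as the time levels of the group x time test for objective (c), stating which televisit supplies the second level in each group.
2. Replace the .95 sentence, for caffeine consumption only, with: *With N = 100 (1:1), two occasions, alpha .05, r = .5, partial eta squared .02 (0.57 SD between-group difference in change) and complete data, group x time power is about .81.* If another effect is intended, state the week-7 difference in SD units and its two-occasion power, for example about .90 for 0.66 SD. Add the value at the expected loss to follow-up.
3. Attach no power figure to symptom outcomes yet. This is a separate conflict to reconcile. Section 7.b says it will "compare this with scores on these assessments at the screening and treatment televisits", and 7.c says summaries of the "standardized assessments in Table 1 will be calculated for screening, treatment, 7 Week Follow-Up". Yet Table 1 marks no symptom scale at the Treatment televisit, and Section 4.a says only that participants there "complete assessments to determine their caffeine consumption and cigarette use over the past 7 days as outlined in Table 1".

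The cost is one reworded sentence and two named time levels, with no added participants or visits. The stated power may become less favourable.

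### Section 7.c claims .95 power for a small effect with 100 participants, but no reading tested gives both: power is about .94 for a medium or larger effect, or about .51 for a small one.

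*Combined protocol and SAP*

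**What the plan says.** Section 7.c (statistical plan and sample size) sets out a mixed effects regression with group, time and their interaction for comparing the immediate and delayed arms. The power inputs follow: "with two groups, four measurements, an alpha of .05, a desired power of .95", then "correlation among repeated measures of .5", then the effect and the conclusion: "conservatively estimating a small effect (e.g., partial eta squared = .02), a sample size of 100 will be sufficient to detect a treatment effect".

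The paragraph does not say which model term the power refers to, how partial eta squared is defined, or what the effect means in SD units or mg of caffeine.

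The same paragraph describes the analysis as mainly descriptive and rests the figure of 100 partly on laboratory capacity. It also plans to calculate Cohen's *d* and "partial eta squared effect sizes using means and standard deviations" for pre- and post-treatment on every secondary outcome, and to size later randomised trials from these values.

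**The concern.** With a correlation among repeated measures as a separate input, a partial eta squared of .02 can mean two quite different effects. It may be set on the raw between-person SD, with the correlation then entering the noncentrality. Or it may be the quantity that a repeated-measures ANOVA usually reports, where the correlation is already in the error term. The two differ by a factor of about 2.7 in noncentrality. Section 7.c does not say which is meant, yet it attaches both a high power and the labels small and conservative to the number.

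Two things are at stake. The first is what the randomised comparison in secondary objective (c) can show: a reader who takes the sentence at face value could treat a null group x time result as good evidence against a small effect. The second is the later trials. If a partial eta squared computed in the usual way is put into a calculation that applies the correlation again, the next trial will be too small. At .02 the two conventions give about 107 and 284 participants.

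**Working it through.** **Inputs from section 7.c.** Groups k = 2; measurements m = 4; alpha = .05; target power .95; correlation r = .5; partial eta squared = .02; N = 100.

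**Assumed, because not stated.** The tested term is group x time; allocation is 50 per group; all four measurements are complete; sphericity holds.

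**Conversion.** f² = .02/(1 − .02) = .0204, so f = .143. The interaction test has (k − 1)(m − 1) = 3 and (N − k)(m − 1) = 98 × 3 = 294 degrees of freedom. Power comes from the noncentral F distribution.

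**Step 1: reproduce the plan's figure (raw-SD scale, correlation applied separately).**
λ = f² × N × m/(1 − r) = .0204 × 100 × 4/.5 = 16.33. Power = .936. Reaching .95 takes N = 107 (108 if even). If f was rounded up to .15 (partial eta squared .022), 98 is enough. So 100 is approximately reproduced.

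**Step 2: the usual repeated-measures scale**, SS effect/(SS effect + SS error).
λ = f² × (N − k) × (m − 1) = .0204 × 98 × 3 = 6.0. Power = .512. Reaching .95 takes N = 284.

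**Step 3: a group main effect instead.** Power is .43 with the correlation adjustment, λ = f² × N × m/(1 + (m − 1)r) = 3.27. It is .29 on the conventional scale, λ = f² × (N − k) = 2.0. Neither is close.

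**Step 4: what the step 1 effect amounts to.** On the usual scale, λ/(λ + error df) = 16.33/(16.33 + 294) = .053. In SD units, let D_t be the group difference at visit t. Then f² = var(D_t)/4, with the variance taken over the four visits (divisor 4). For a peak difference δ:

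| Pattern of the difference | var(D_t) | δ giving f² = .0204 |
|---|---|---|
| At two of four visits | δ²/4 | 0.57 SD |
| At one or three visits | 3δ²/16 | 0.66 SD |
| Linear divergence, δ at last visit | 5δ²/36 | 0.77 SD |

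Simulated 2 × 4 repeated-measures ANOVAs (4,000 runs, 50 per group) gave power .93 at 0.571 SD on two visits and .94 at 0.66 SD on one visit.

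**Step 5: what a small effect gives.** A usual partial eta squared of .02 corresponds to 0.35 SD (two visits) or 0.40 SD (one visit); simulated power was .51 and .50. A difference of 0.2 SD gave simulated power .19 (two visits) and .15 (one visit).

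**Step 6: why a pattern must be stated.** At 0.6 SD, the step 1 formula gives .957 (two visits), .879 (one or three visits) or .755 (linear).

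**The case against.** The strongest reply is that section 7.c documents no error. Setting an effect on the between-person SD and entering a correlation separately is a coherent way to specify a power calculation, and listing the correlation as an input points that way. This stands. A reader might infer that the correlation has been counted twice, but the plan names no convention and does not say that .02 came from a repeated-measures analysis. The raw-SD reading is inferred only because it alone comes near the stated power.

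A reader might also infer that the label small is wrong whichever convention applies. It is not: on the usual scale .02 can fairly be called small, and there the power is what fails. Nor can it be shown that the value is not conservative relative to the effect expected, since the background section reports significant reductions in two earlier trials without effect sizes.

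It is tempting, too, to say that the plan will report its effects on the usual repeated-measures scale. The text does not go that far. It promises pre- and post-treatment effect sizes from means and standard deviations, with no stated error term, and plans no comparison of them with the planning value.

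Finally, this is a pilot. The comparison is secondary, the analysis is mainly descriptive, and 100 also rests on capacity. That limits the consequences, and a misread null result is a risk rather than a planned inference. It does not make the power sentence correct.

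**Conclusion.** The point holds in this form: no reading tested delivers both a small effect and .95 power with 100 participants. Either power is about .94 for an effect of 0.57 to 0.77 SD depending on the visit pattern (usual partial eta squared about .05), or the effect is small and power is about .51.

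The figures assume a group x time test, equal allocation, four complete measurements, sphericity and r = .5. The arithmetic is firm under those assumptions; the convention the authors used is not known. The sentence should be corrected. The importance is moderate, because no primary objective and no participant number depends on it.

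**What to change.** Keep 100 participants and replace the power sentence in section 7.c with:

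> For the group x time test with 100 participants, four complete measurements, r = .5 and alpha .05, power is about .94 for a between-group difference of 0.57 SD present at two of four visits or 0.66 SD present at one or three visits (repeated-measures partial eta squared about .05), about .5 for repeated-measures partial eta squared .02, and below .2 for a difference of 0.2 SD.

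Delete the phrase that presents the effect as a conservative estimate of a small one. Where the paragraph says that the trial's effect sizes will be used to size future trials, state which partial eta squared convention will be used, so that the value can be entered into the matching formula.

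The cost is a change of wording and a less favourable stated figure. The design, the visits and the number of participants do not change.

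### The delayed group has no symptom score scheduled at its 7-week comparison point, so secondary objective (c) cannot be answered for symptoms; in addition, later trials are to be sized from pre-post rather than randomized effects

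*Combined protocol and SAP*

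**What the plan says.** **The randomized comparison.** Section 2, secondary objective (c), sets the immediate group at 7 weeks, for both caffeine use and caffeine-related problems, "relative to the delayed treatment group at 7-weeks post-enrollment (prior to delayed treatment". The purpose given is to "compare the initial efficacy of our intervention with caffeine reductions that may occur spontaneously over the same duration". Section 7.b repeats this for all the secondary outcomes, in order to "compare our intervention relative to spontaneous reduction that may occur with the passage of time". For objective (b), section 7.b also sets follow-up symptom scores against scores at both the screening and the treatment televisits.

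**The schedule.** Section 4.a gives the delayed group a treatment "visit scheduled for a date approximately 7 weeks after screening". For that televisit it lists past-week caffeine and cigarette assessments, and Table 1 marks the same kinds of measure and nothing else. Of the weekly surveys, section 4.a says: "At seven days following the treatment televisit, participants will receive a request to complete a survey via Qualtrics link". The Week 7 televisit is also counted from treatment, not from enrollment.

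**The effect sizes.** Section 7.c says: "With respect to comparisons between the immediate and delayed intervention group, we will use a mixed effects regression model", with group, time and their interaction. It then adds Cohen's d and partial eta squared as "effect sizes using means and standard deviations for pre-and post-treatment for all secondary outcomes", and continues: "These effect size calculations will be used to determine the necessary sample size for any future large-scale randomized controlled trials".

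**The concern.** Seven weeks after enrollment, the delayed group is at its treatment televisit and still untreated. This is the only scheduled contact at which it can serve as a control. If no symptom scale is given there, the randomized design yields a controlled estimate for caffeine use and none for anxiety, sleep or gastrointestinal symptoms. The abstract says that earlier in-person trials did not measure improvement in these symptoms, so this is much of what the new trial could add.

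The planning issue is separate and milder. A later randomized trial is powered on a difference between arms. A pre-post effect size contains whatever change would have happened anyway, and the protocol says that randomization is there to separate that change out. The plan nevertheless names the pre-post quantity as the planning input and gives the randomized contrast no such role.

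**Working it through.** **1. Symptom scores in the delayed group, from Table 1 and section 4.a**

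| Contact | Delayed group, approximate time | Symptom scales scheduled |
|---|---|---|
| Preliminary online screening | before screening, interval not stated | PROMIS scales |
| Screening televisit | week 0 | GAD-7, Pittsburgh Sleep Quality Index, Insomnia Severity Index, GSRS, Caffeine Use Disorder Questionnaire |
| Treatment televisit | week 7, untreated until the manual is given | none |
| Weekly surveys 1-6 | weeks 8-13, treated | PROMIS scales |
| Week 7 televisit | week 14, treated | all of the above |

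The times follow from treatment at about week 7 after screening, plus 1 to 6 weeks for the surveys and 7 weeks for the follow-up televisit.

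The promised contrast needs the immediate group at its Week 7 televisit (7 to 8 weeks after screening, treated) against the delayed group at about week 7 (untreated). The first cell is filled and the second is empty. Comparing both groups at their own Week 7 televisits does not replace it: both are then treated, and the delayed group is about 14 weeks from screening. The treatment-televisit symptom comparison in section 7.b fails for the same reason, in both groups.

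Caffeine use is different. The timeline follow-back and the past-7-days survey are marked at the screening, treatment, Week 7 and Week 14 televisits, so its controlled contrast can be computed.

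**2. The plan's own power figure**

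Inputs from section 7.c: two groups, four measurements, alpha .05, correlation .5, partial eta squared .02, N = 100, power .95. For the group-by-time interaction:

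- f² = .02/.98 = .0204
- λ = f² × N × 4/(1 − .5) = 16.33, on 3 and 3 × 98 = 294 degrees of freedom
- power = .936, close to the stated .95

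The figure reproduces approximately, and the present point does not depend on it. Its four measurements match the televisits for caffeine use. The GAD-7, sleep, insomnia and GSRS scales are scheduled at three.

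**3. What pre-post planning could do, for caffeine use only**

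The documents give no spontaneous share s of the pre-post change. I assume 5, 10 and 20%, a later trial with an untreated or wait-list comparator, and r = .5 (the plan's value). At r = .5 the change SD equals the raw SD, because √(2(1 − r)) = 1, so the unstated standardizer makes no difference here. Then controlled d = (1 − s) × pre-post d. For a later trial sized at 80% power on the pre-post d:

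- analysed unadjusted: power = Φ(2.802(1 − s) − 1.96)
- baseline-adjusted, variance factor 1 − r² = .75: power = Φ(2.802(1 − s)/√.75 − 1.96)

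| s | Unadjusted | Adjusted |
|---|---|---|
| 5% | 76% | 87% |
| 10% | 71% | 83% |
| 20% | 61% | 74% |

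Adjusted power stays at or above 80% until s = 1 − √.75, about 13%.

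**4. Precision of the randomized estimate**

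Assume d = .5, 50 per group (the allocation ratio is not stated) and no dropout. The 95% half-width is 1.96 × √(2a/n + .25/(4n)).

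- Unadjusted (a = 1): .398, so 0.10 to 0.90. At 80% power this corresponds to 1,571 down to 21 per arm.
- Adjusted at r = .5 (a = .75): .346, so 0.15 to 0.85, or 699 down to 23 per arm.

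**The case against.** **Table 1 may not be decisive.** Sections 7.b and 7.c promise symptom scores at the treatment televisit, so the documents conflict about what is collected. Table 1 also departs from the text elsewhere: it marks observer ratings under the weekly surveys and Week 14, while section 4.a places them near treatment and Week 7. The Measures document is not available here. This stands as a reason to ask for reconciliation. It does not remove the gap, because the prose of section 4.a independently lists only caffeine and cigarette assessments at that televisit.

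**This is a mainly descriptive pilot, and later trials would have their own approval (section 4.f).** This is true, and it makes the planning point correctable later for caffeine use. It does not help with symptom scores that were never collected.

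**The effect-size sentence might cover between-group quantities.** It applies to all secondary outcomes, and these are compared between groups. A reader might infer that the plan rules out using the randomized estimate. It does not; it is silent. The literal wording nevertheless defines the effect sizes on pre- and post-treatment values.

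**The randomized estimate is imprecise, and later trials may involve other populations.** Both objections stand. An interval from 0.15 to 0.85 cannot fix a sample size.

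**A reader might infer that later trials will be underpowered.** The documents do not support that. Section 3 reports that effects in the earlier in-person trial were attributed to the manual rather than to the passage of time, so the spontaneous share may be small. With baseline adjustment, any shortfall at 5 to 10% disappears.

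**Conclusion.** The symptom part is wrong as written. Under the schedule in Table 1 and section 4.a, secondary objective (c) cannot be answered for symptoms, and the treatment-televisit symptom comparison in section 7.b cannot be made. The conclusion rests on the schedule being followed as stated. It does not extend to caffeine use, for which the randomized comparison remains available, nor to the primary feasibility outcome or participant safety.

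The planning part is a cheap improvement and not a demonstrated bias. Its size depends on an assumed spontaneous share, an assumed comparator, and whether the later trial adjusts for baseline. Because the standardizer is not named, even the direction for caffeine use would depend on the pre-post correlation if a change SD were used. No direction or size is claimed for symptom scales.

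**What to change.** **Symptoms.** Add the existing questionnaires (PROMIS scales, GAD-7, Pittsburgh Sleep Quality Index, Insomnia Severity Index, GSRS and Caffeine Use Disorder Questionnaire) to the treatment televisit, before the manual is given, at least for the delayed group. Reconcile Table 1 and section 4.a with sections 7.b and 7.c. Otherwise, state in sections 2, 7.b and 7.c that no treatment-televisit or controlled symptom comparison will be available. Adding the scales costs a few questionnaire minutes at one existing televisit. It has to be done before delayed participants reach that visit.

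**Planning effect size, caffeine use.** In section 7.c, take it from the baseline-adjusted difference between the immediate group at its Week 7 televisit and the delayed group at its treatment televisit, divided by the screening SD, with a 95% CI. Plan on the interval and not on the point estimate alone. Keep the pre-post d and partial eta squared as descriptive, and name the pre-treatment visit (screening or treatment televisit, about 7 weeks apart in the delayed group) and the standardizer. This is a change of wording only, since both assessments are already scheduled. The downside is imprecision: the estimate can only bound later sample sizes.
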